All analyses will be intention-to-treat analyses—that is, data from parents and children will be analyzed based upon the condition to which they will be initially assigned, regardless of the number of classes they attended. This approach, although it reduces power, maintains the internal validity of the RCT design.⁵⁷ Because participants will be nested within classes, the intraclass correlations (ICC's) will be first examined for each dependent variable to determine if a statistical approach controlling for such nesting will be necessary. All outcome variables (except for child weight status) will be examined using multilevel analyses with the SPSS (version 25) Mixed Models Program. The SPSS Mixed Model program does not provide measures of effect sizes; however, 95% confidence intervals will be included for precision. Child sex, child age in months, and child BMIz at pre-test will be control variables in all of the multilevel analyses. Significant condition by time interactions will be followed up with simple main effects analyses and multi-level analyses comparing pairs of time points. The main analyses will be conducted on participants who have data at all 4 time points. Paired comparisons will use all available data. Most of the missing data will be addressed by calculating the subscale scores using the mean of the non-missing items in that particular subscale. If greater than 25% of a subscale's items are blank, then the score will be considered missing. The multilevel models also will be rerun examining (1 at a time) possible program moderators: child age, child sex, child BMI status, and location (Houston versus Pasco). Moderation will be tested by examining the significance of the moderator by condition by time interactions.

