Finally, to examine dosage effects, the multilevel analyses will be rerun for those variables showing significant condition by time interactions. In these analyses, only data from parents in the prevention conduction at post-test, 6-months, and 12-months will be examined to determine if the number of sessions parents attended predict their subsequent responses on questionnaire assessments (the pre-test assessments will not be included in these analyses because these sessions occurred *before* parents attend any classes). In conducting these analyses, the condition variable will be replaced by a variable assessing the number of lessons attended (values ranging from 0 to 7). To determine if the dosage effects vary by time point, a separate set of analyses will include the “lessons attended by time” interaction as a predictor (along with the corresponding main effects).

A multinomial logistic regression will be used to examine the effects of the program on children's BMI category (i.e., healthy weight, overweight, and obese). This regression will examine the main effect of condition, controlling for the same variables as in the multilevel

analyses (i.e., child sex, child age in months, and child BMI *z*-score at pretest).

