To control for Type I error, the critical *p* values for each assessment will be determined with the unweighted Bonferroni method,⁵⁸ dividing the critical value of *p* < .05 by the number of comparisons conducted for a given assessment. As discussed in Shaffer,⁵⁸ corrections for familywise error involve correcting alphas separately for each family of hypotheses. Although defining families is a rather straightforward process in a simple experiment (e.g., 1 family in a study with a single dependent variable and 1 independent variable with several levels), Shaffer argues that defining families becomes more complicated (and potentially more problematic) in large, more complex studies where alpha corrections can substantially lower statistical power (i.e., increase Type II error). To balance concerns about Type I and Type II error, a family will therefore be defined as the set of measures derived from a particular outcome assessment, and an alpha correction procedure will then be used (the unweighted Bonferroni) to control for error-rates within families. The resulting critical *p* values will be: FPI, 0.05/16 = 0.003; CFSQ, 0.05/3 = 0.017; FKQ, 0.05/6 = 0.008; compensation trials, 0.05/1 = 0.05; EAH, 0.05/1 = 0.05; FPQ, 0.05/2 = 0.025; CEBQ, 0.05/8 = 0.006; BMI, 0.05/2 = 0.025. Only results that meet these critical values will be reported in the primary analyses. To minimize the probability of Type II error, these critical values will be applied only to *p* values for the simple main effects analyses of time given the limited power of condition by time interactions in this type of design.⁵⁹

Finally, exploratory analyses will be run on variables that show condition by time interactions in the pre-post analyses reported by [name] and colleagues⁴⁵ but do not show significant interactions in the current study. Because the smaller samples at follow-up may reduce the power to find significant time by condition interactions at 6- and 12-months, simple main effects analyses of time were be run separately for the control and prevention groups to determine if the condition effects found in earlier pre-post analyses¹⁶ persisted for the variables in the current study.

REFERENCES

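### The main condition-by-time tests use only families seen at all four assessments, and these tests decide which outcomes are followed up; no visit-level missing-data assumption or sensitivity analysis is planned

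*Combined protocol and SAP*

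**What the plan says.** All references are to the combined protocol and SAP.

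- **Label (Data Analyses).** "All analyses will be intention-to-treat analyses", which the plan explains as analysis by assigned condition, "regardless of the number of classes they attended".
- **Main set.** "The main analyses will be conducted on participants who have data at all 4 time points".
- **Follow-up of the main test.** "Significant condition by time interactions will be followed up with simple main effects analyses and multi-level analyses comparing pairs of time points". For these, "Paired comparisons will use all available data".
- **Dosage analyses.** "the multilevel analyses will be rerun for those variables showing significant condition by time interactions".
- **Power.** The Bonferroni paragraph leaves the interaction tests uncorrected because of the "limited power of condition by time interactions in this type of design". The final paragraph expects that "smaller samples at follow-up may reduce the power", and answers with exploratory tests of time within each arm, for outcomes that had an interaction in the earlier pre-post report.
- **Timing.** Families are randomised after pretest (Participant Eligibility and Recruitment). Posttest, 6 months and 12 months come later (Study Design).
- **Missing data.** Apart from the two rules on who is analysed, the plan gives only an item-level rule: subscale means over answered items, and a missing score if more than 25% of items are blank.

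**The concern.** A family enters the main test only if it is observed at three assessments after randomisation. Analysing by assigned arm does not by itself protect a subset formed in that way. The prevention arm is asked to attend seven weekly lessons and the control arm none, so reasons for leaving could differ between arms.

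The all-available paired comparisons are a partial safeguard, but an outcome reaches them only through a significant completer interaction. An outcome that misses there gets neither the paired follow-up nor the dosage analysis. The exploratory analyses bring back only outcomes with an earlier pre-post interaction, and they do not compare the arms.

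The plan thus discards observed visits from the test whose power it already regards as limited. The mixed models that it specifies do not require complete records.

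**Working it through.** **Inputs.** The documents give no total sample size, effect size, SD, correlation or dropout rate, so there is no figure of the plan to reproduce. Assumed throughout unless stated: 100 per arm, outcome SD 1, visit correlation 0.6 (exchangeable or AR(1)), loss m = 5, 10, 15 or 20% at each follow-up visit, class nesting ignored, test at 0.05.

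**1. Who is left.** The completer share is (1−m)³ = 0.857, 0.729, 0.614, 0.512. The share of observed follow-up visits discarded is:

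- permanent dropout: 1 − 3(1−m)³/[(1−m)+(1−m)²+(1−m)³] = 0.051, 0.103, 0.157, 0.213;
- intermittent misses: 1 − (1−m)² = 0.10, 0.19, 0.28, 0.36.

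**2. Power of the 3-df interaction test, permanent dropout unrelated to outcome.** With q = 1−m, the shares of families last seen at pretest, posttest, 6 and 12 months are m, qm, q²m and q³. The information per arm is 100 × the sum over patterns of share × inverse covariance of the observed visits; the completer analysis keeps only the q³ term. Let V be twice the inverse of that information and L the three differences from pretest. For mean differences d between arms, λ = (Ld)ᵀ(LVLᵀ)⁻¹(Ld), and power = P(χ²₃(λ) > 7.815).

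Check by hand for completers, exchangeable, m = 10%, 0.4 SD at all three follow-ups. Changes from pretest have variance 0.8 and covariance 0.4, so the quadratic form is 0.16 × (1/0.4) × (3 − 9/4) = 0.30. Then λ = (72.9/2) × 0.30 = 10.9, and power is 80.1%.

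Power in %, completers / all observed data:

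| Effect at posttest, 6, 12 months (SD) | Correlation | 5% | 10% | 15% | 20% |
|---|---|---|---|---|---|
| Sustained: 0.4, 0.4, 0.4 | Exchangeable | 86.7/90.0 | 80.1/88.0 | 72.2/85.7 | 63.4/83.0 |
| | AR(1) | 72.1/77.5 | 64.2/75.5 | 56.0/73.3 | 47.9/70.9 |
| Gradual: 0, 0.2, 0.4 | Exchangeable | 83.3/84.2 | 76.2/78.4 | 68.0/71.5 | 59.2/64.0 |
| | AR(1) | 49.7/51.9 | 43.0/47.0 | 36.7/42.1 | 31.0/37.3 |
| Late: 0, 0, 0.4 | Exchangeable | 86.7/86.9 | 80.1/80.6 | 72.2/73.0 | 63.4/64.4 |
| | AR(1) | 72.1/72.9 | 64.2/65.9 | 56.0/58.4 | 47.9/50.7 |

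The loss is about 3-23 points for a sustained effect, 1-6 for a gradual one and 0-3 for a late one. Simulation with estimated covariance agrees closely (sustained, exchangeable, 10%: 78.6/87.1). With intermittent misses the simulated loss for a sustained effect runs from about 6 points at 5% loss (84.5/90.6, exchangeable) to 27 at 20% (47.0/74.3, AR(1)).

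**3. Bias of completer changes (simulated, SD units).**

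- *No effect, prevention-arm dropout depending on posttest score, control dropout random:* 0.02 to 0.11 for pre-to-post change, about 0 at 6 months, 0 to −0.06 at 12 months.
- *No effect, dropout depending on the previous observed value differently by arm (exchangeable, 100,000 per arm):* about −0.11 to +0.05 at 12 months; likelihood on all observed data stayed within about 0.01 of the full-data result.
- *One identical posttest-dependent rule in both arms:* within 0.007 under no effect; −0.01 to −0.02 for pre-post change under a 0.4 SD effect.
- *No effect, prevention-arm dropout depending on a stable family level:* completer changes within 0.002; the missing-at-random likelihood off by about 0.01 to 0.06 at 6 and 12 months.

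**The case against.** **The power cost depends on the shape of the effect.** This stands. If the effect emerges only at 12 months, families who leave earlier carry little information about it, and the completer rule costs almost nothing. A reader might infer from the sustained-effect rows that the rule costs 20 points or more. The documents give neither the effect shape nor the attrition that this would need.

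**The paired comparisons already use everyone available.** This stands in part. In the scenarios where all dropout comes after posttest, the all-available pre-post comparison loses nobody, so the 0.02-0.11 SD figure bears on the completer interaction test and not on that paired estimate. But the safeguard operates only after the completer test is significant.

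**The plan does not break its own definition of intention-to-treat.** This also stands. The definition concerns assigned condition and attendance, and the plan claims internal validity for that approach, not for the completer rule. A reader might infer a self-contradiction. The definition is met, and what remains is mostly terminology: the usual all-randomised meaning is wider.

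**Inflated false positives.** A reader might infer these too. In the no-effect runs with posttest-dependent dropout in the prevention arm, the completer interaction alone rejected in 5.5-12.8% of runs. Also requiring a significant all-available contrast against pretest (unadjusted 5%) brought this to 3.5-5.8%. If any of the six pairs may count, it is 5.5-11.7%. The plan does not name the pairs and applies Bonferroni limits to the simple effects of time, so none of these is the trial's error rate.

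**Conclusion.** The concern holds as a design weakness that should be fixed. A completer test, on a subset selected after randomisation, decides which outcomes are followed up, and no visit-level assumption, dropout comparison by arm or sensitivity analysis supports it. That rests on the text alone.

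The size rests on assumptions. The power cost ranges from near zero to about 23 points with permanent dropout, depending on effect shape and loss rate, and is somewhat larger with intermittent misses.

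Bias is possible but not shown. It was roughly up to 0.1 SD where outcome-related dropout differed by arm, with sign and time point set by the assumed mechanism. Under one identical rule in both arms it was about zero with no effect and up to about 0.02 SD with a 0.4 SD effect. The documents report no differential dropout, so they do not support a reading that the trial's estimates are biased.

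**What to change.** 1. Fit the main mixed models to every randomised family with any outcome data, using all observed time points (for example REML with unstructured covariance), and state the missing-at-random assumption.
2. Derive the paired contrasts from the same model, and name the pairs that will be read.
3. Keep the four-visit completer analysis as a sensitivity analysis and report both results.
4. Report missed visits and dropout by arm and time point.
5. Optionally, clarify that intention-to-treat here refers to assigned condition, or reserve the term for the all-randomised analysis.

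The cost is SAP wording, a re-run of the same SPSS procedure and one table. The downside is reliance on missing at random. When dropout depends on a stable family level, that analysis can be slightly biased (about 0.01-0.06 SD in the assumed scenarios) where completer change scores would not be. Neither analysis is unbiased under every mechanism, which is why both should be shown.

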The goal of this study is to develop and test the efficacy of a scientifically-based, culturally competent seven-session parent directed, obesity prevention program focused on parental feeding strategies that support young children's self-regulation of intake.

STUDY DESIGN

A randomized controlled trial will be implemented across 2 sites (Houston, an urban city in Texas; and Pasco, an agricultural community in Washington) to examine the efficacy of the SEEDS childhood obesity prevention program. The prevention arm will receive parent and child program curriculums separately over 7 weeks for a total of 7 lessons. One lesson will be held each week with parent and child lessons held simultaneously. Each lesson will last about an hour. A combined family lesson (parent and child together) will be held before the parent and child lessons. All lessons will be held after the school day in Spanish at Head Start centers in Houston, TX and similar early education centers in Pasco, WA. The control arm will receive no curriculum. Approximately 8 to 10 families will participate in each of the prevention and control conditions at each wave. Parents will be asked if they could read and write in English or Spanish during eligibility screening so that assistance can be made available at the data collection sessions for those who need help completing the questionnaires. Participants in the prevention and control arms will complete the same assessments prior to the prevention program (pretest), after the program (posttest), and at 6- and 12-month follow-ups. Participants will be compensated \$40 at pretest, \$50 at posttest, \$60 at 6 months, and \$85 at 12 months.

FACILITATORS

Bilingual staff members will lead the face-to-face groups (i.e., parent, child, and family lessons). Parent facilitators will be required to have a graduate degree in psychology or education to optimize behavior change that is integrated into the program content. Child facilitators will be required to have training or experience in early childhood education. Family lessons will be co-facilitated by the parent and child facilitators. Facilitator training will include a 2-day intensive training session guided by study investigators which will include coverage of the program

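### The dosage analysis leaves out parents' pretest scores, so a difference in starting level can pass for an effect of lessons attended

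*Combined protocol and SAP*

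**What the plan says.** The dosage analysis is set out in the DATA ANALYSES section of the combined protocol and SAP, after the main models.

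- **Outcomes entering it:** "the multilevel analyses will be rerun for those variables showing significant condition by time interactions".
- **Data:** "only data from parents in the prevention conduction at post-test, 6-months, and 12-months will be examined".
- **Exposure:** "the condition variable will be replaced by a variable assessing the number of lessons attended", scored 0 to 7.
- **Aim:** to find out whether the "number of sessions parents attended predict their subsequent responses on questionnaire assessments".
- **Pretest:** "the pre-test assessments will not be included in these analyses because these sessions occurred" before parents had attended any class.
- **Covariates:** "Child sex, child age in months, and child BMIz at pre-test will be control variables in all of the multilevel analyses".

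A separate set of models adds the interaction of lessons attended with time. Under STUDY DESIGN, participants in both arms "will complete the same assessments prior to the prevention program (pretest), after the program (posttest), and at 6- and 12-month follow-ups", so each measure has a pretest value. Nothing in the document brings that value back into the dosage models, either as a covariate or through a change score.

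**The concern.** Randomisation fixes the arm, not how many lessons a family attends. Within the prevention arm, attendance is an observational exposure, and the parent's starting level on the outcome is an obvious potential confounder. Because it is measured before the first lesson, attendance cannot have affected it, and this is what makes it suitable for adjustment. The plan's reason for excluding pretest shows only that it is not an outcome of attendance.

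In the main models pretest is one of the four time points, so the condition-by-time term takes starting level into account. Dropping the pretest rows for the dosage models removes the only place where it enters. Child sex, age and BMIz do not replace a parent's starting score on a feeding questionnaire. A random intercept does not either, because it assumes that differences between parents are unrelated to attendance.

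The trial could therefore report that more lessons bring better feeding practices when the parents already differed before lesson one. If parents with poorer practices attend more, a real dose effect could be masked instead.

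**Working it through.** The plan gives no sample size, power or effect size for this analysis, so there is no figure to reproduce. The question is how often the planned model would show a dose effect when there is none.

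**Inputs from the document:** prevention arm only; three post-programme time points; lessons 0 to 7; pretest score omitted. The Bonferroni limits are reserved for the simple main effects of time, so a two-sided 0.05 is used here.

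**Assumed inputs:** n = 60, 100 or 150 prevention-arm parents; correlation ρ = 0.5 to 0.7 between any two measurements of the outcome; correlation r = 0 to 0.3 between attendance and pretest; lessons centred near 4.5 with SD about 2, then rounded and cut to 0-7. Child covariates and class nesting are left out, and the mean of the three follow-up scores is regressed on lessons attended.

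**Step 1, check by formula.** With each score scaled to SD 1, the mean of three follow-ups has variance ρ + (1 − ρ)/3. Its correlation with pretest is c = ρ / √(ρ + (1 − ρ)/3). For ρ = 0.6, c = 0.6 / √0.733 = 0.70. If attendance is linked to the outcome only through pretest, its correlation with follow-up is r × c. The rejection rate is approximately Φ(√(n − 3) × atanh(rc) − 1.96). For n = 100 and r = 0.3: rc = 0.21, atanh = 0.213, 9.85 × 0.213 = 2.10, and Φ(0.14) = 56%. The simulated value is 53%; rounding and truncating lessons weakens the correlation slightly.

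**Step 2, simulation with no true dose effect, n = 100** (4,000 data sets per setting for ρ = 0.5 and 0.7; 1,500 for ρ = 0.6):

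| r | Pretest omitted, ρ = 0.5 | ρ = 0.6 | ρ = 0.7 | Spurious 0-versus-7-lesson difference (ρ = 0.5 to 0.7) | Pretest included |
|---|---|---|---|---|---|
| 0 | 4.4% | not run | 5.1% | about 0 | 4.6-5.2% |
| 0.1 | 8.6% | 12.0% | 11.7% | 0.18-0.26 SD | 5.0-6.1% |
| 0.2 | 21.8% | 26.7% | 32.9% | 0.37-0.52 SD | 4.8-5.9% |
| 0.3 | 43.4% | 53.0% | 64.3% | 0.56-0.79 SD | 4.4-4.5% |

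The spurious difference is seven times the mean slope per lesson. At r = 0.3, for example, 7 × 0.080 = 0.56 SD and 7 × 0.113 = 0.79 SD.

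**Step 3, other arm sizes.** For r = 0.1 to 0.3 and ρ = 0.5 to 0.7, the rate with pretest omitted runs from 7.1% to 44.3% at n = 60 and from 11.4% to 80.3% at n = 150. A larger arm does not cure the bias; it makes a false finding more likely.

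**Step 4, a harder case.** Suppose attendance follows the parent's underlying level, which the questionnaire measures with reliability 0.6. Attendance then correlates r / √0.733 with mean follow-up: 0.117, 0.234 and 0.350 for r = 0.1, 0.2 and 0.3. The partial correlation given pretest is (r/√0.733 − 0.70r) / √((1 − r²)(1 − 0.70²)), or about 0.07, 0.13 and 0.21. Simulation at n = 100 gives false dose effects in 21%, 64% and 95% of analyses without pretest and 9%, 26% and 51% with it.

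**The case against.** The strongest objection is that the bias is conditional and its condition is not documented. Nothing in the plan shows that attendance is related to starting scores, and with r = 0 the planned analysis holds its 5% level. This stands: the omission is certain, but the size of any bias is not.

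Second, the parenthesis on pretest may mean only that pretest is not a response row, and the plan does keep pretest BMIz as a covariate. That reading is fair, but the covariate list still lacks the pretest score of the outcome, so the same addition is needed.

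Third, the lessons-by-time test is much less exposed. A constant difference between parents cancels between time points; in simulation with a stable parent trait that test stayed at 4.5-5.7% without pretest. It is biased only if the influence of pretest changes over follow-up. This also stands: the exposed quantity is the overall lessons effect.

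Fourth, adjustment returns the error rate to about 5% only if attendance depends on the observed score. In the harder case of step 4 it helps substantially but does not restore 5%, and unmeasured factors such as motivation remain. This is a reason to label the result as observational as well as to adjust; it is not a reason to omit the covariate.

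Finally, the analysis is secondary, is run only for outcomes with a significant condition-by-time interaction, and cannot alter the randomised comparison. That limits the consequence but does not make the dosage result interpretable.

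**Conclusion.** The concern holds. As planned, a non-randomised exposure is related to later scores without the parent's starting level on the same measure, and the stated reason does not justify that. Under the assumptions listed, even a modest attendance-pretest correlation of 0.2 would raise the false-positive rate from 5% to roughly 22-33% with 100 parents, with an apparent difference of about 0.4 to 0.5 SD between no lessons and all seven. A negative correlation would bias the estimate the other way. If the correlation is zero there is no bias, and the documents neither show nor exclude one. The plan should be changed, because a reader would take a positive dosage result as support for the programme. The main randomised findings do not depend on it.

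**What to change.** Keep post-test, 6 months and 12 months as the outcomes. Add each parent's pretest score on the same measure as a covariate in every dosage model, including those with the lessons-by-time term. In the latter, a pretest-by-time term is also needed if the interaction itself is to be protected, because a pretest main effect alone leaves that contrast essentially unchanged.

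Report attendance against pretest scores and other baseline characteristics, so that readers can see whether the two are related. Describe the result as an observational association within the prevention arm, and exempt this analysis from the statement that all analyses are by intention to treat.

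The cost is SAP wording and one covariate (two model terms where the time interaction is used). Pretest is completed before randomisation, so no new data collection is needed.

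### The child weight model names no visit, its two BMI comparisons are unlabelled, and the 0.025 set for BMI conflicts with the rule on where thresholds apply

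*Combined protocol and SAP*

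**What the plan says.** Data Analyses treats weight apart from everything else: "All outcome variables (except for child weight status) will be examined using multilevel analyses". The only weight model is then given: "A multinomial logistic regression will be used to examine the effects of the program on" a three-level BMI category. "This regression will examine the main effect of condition, controlling for the same variables" as elsewhere, namely sex, age and pretest BMI z-score. The model has no time term and no stated visit. Study Design plans a pretest, a posttest, and follow-ups at 6 and 12 months.

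The multiplicity paragraph of Data Analyses divides 0.05 by the number of comparisons for each assessment and treats the measures from one assessment as a family. For weight it lists "BMI, 0.05/2 = 0.025". It keeps results that miss their threshold out of the primary report. It then limits the thresholds to simple main effects of time, because condition by time interactions have little power in this design.

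Under Measures (Anthropometrics), a BMI z-score is derived for each child. The lowest child category starts at the 5th percentile, whereas for parents low and normal weight form one class. The one stated analysis role for BMI z-score is as a covariate: "Child sex, child age in months, and child BMIz at pre-test will be control variables in all of the multilevel analyses", and likewise in the weight model.

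**The concern.** Four things about the weight result are left open: the visit, the two comparisons, the test to which 0.025 applies, and the handling of children below the lowest category. Because primary reporting depends on meeting the threshold, whether the weight result appears at all is open too. Each of these could be settled after the data are seen. In an obesity prevention trial, readers will look for this result even though the plan does not call it primary.

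A second matter is information. Category ignores change within a category. BMI z-score uses it, is already derived, and is not analysed at follow-up.

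**Working it through.** **1. The plan's own figure.** 0.05/2 = 0.025, exact. The other thresholds also reproduce after rounding: 0.05/16 = 0.0031, 0.05/3 = 0.0167, 0.05/6 = 0.0083, 0.05/8 = 0.00625. The arithmetic is not at fault.

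**2. What the divisor 2 can mean.** Three readings fit:
- two logits (3 categories − 1 = 2);
- BMI category plus BMI z-score (the food preference questionnaire has the same divisor, and Measures names its two scores);
- child plus parent BMI.

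All give 0.025, so the number cannot show which was meant. Both logits plus BMI z-score would make three tests: 0.05/3 = 0.0167.

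**3. The restriction taken literally.** The weight model has one program effect, condition, and no simple main effect of time. The number of its tests under 0.025 is therefore zero. What follows depends on the test used:
- one overall 2-df test of condition at 0.05: error 5%;
- two logits at 0.05 each, one visit: 1 − 0.95² = 9.75% under independence;
- two logits at 0.025 each, one visit: 1 − 0.975² = 4.9%;
- two logits at 0.05 at all three post-baseline visits: 1 − 0.95⁶ = 26.5% under independence. The plan does not announce this; its wording does not exclude it.

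**4. What BMI z-score would add.** The documents give no total N, SD, correlation or effect, so these are assumptions: 100 per arm, BMI z-score SD 1.1, pretest to follow-up correlation 0.85, one visit. Overweight or obese prevalence is 26% (Background) or 40% (assumed upper value). BMI z-score was tested by linear regression on arm, pretest value, age and sex. Category was tested by the 2-df likelihood-ratio test in a multinomial model with the same covariates. There were 2,000 simulated trials per row (Monte Carlo error at most 1.1 points). Heavier means at or above the 85th percentile.

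| True effect (prevalence) | BMI z at .05 | Category at .05 | At least one of the two at .025 | Pair minus category |
|---|---|---|---|---|
| All children 0.23 (26%) | 79.2% | 32.7% | 73.1% | +40.4 |
| All children 0.23 (40%) | 78.8% | 36.5% | 71.8% | +35.3 |
| Heavier only 0.23 (26%) | 10.8% | 14.2% | 14.3% | +0.1 |
| Heavier only 0.23 (40%) | 19.8% | 19.8% | 19.9% | +0.1 |
| Heavier only 0.5 (26%) | 32.9% | 46.2% | 43.5% | −2.7 |
| Heavier only 0.5 (40%) | 64.2% | 62.7% | 66.8% | +4.1 |
| None (26%) | 5.2% | 6.2% | 5.5% | |
| None (40%) | 5.6% | 5.4% | 5.7% | |

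For smaller shifts in all children, same base case, the pair against category alone gives:
- 0.15: 37–38% against 17–20%;
- 0.10: 18% against 11–13%, a gain of about 5 to 7 points;
- 0.05: about 9% against 7–8%, a gain of 0 to 2 points.

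**5. Children without a category.** In these simulations 1.4% to 4.7% of children fall below the 5th percentile at follow-up: 200 × 0.014 ≈ 3 to 200 × 0.047 ≈ 9 of 200.

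**6. Nesting.** This was not simulated. With classes of 9 (Study Design: 8 to 10) and an assumed ICC of 0.01 to 0.05, the design effect 1 + 8 × ICC is 1.08 to 1.40, so 100 per arm acts like 93 to 71.

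**The case against.** **The threshold.** A reader might infer that 0.025 governs nothing in the weight model. That rests on one sentence, whose stated reason (weak condition by time interactions) belongs to the multilevel models. The same paragraph assigns 0.025 to BMI by name and ties reporting to it, so the authors may well have meant it for the condition contrasts. This stands: the documents support an internal conflict, not a settled absence of any threshold.

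**The pair.** It is tempting to read the two comparisons as category plus BMI z-score. Two logits fit the rule of counting comparisons equally well, and parent BMI is measured too. Giving BMI z-score half of alpha by default could redefine the family after the fact. This also stands.

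**The power gain.** A shift of 0.23 favours BMI z-score. The residual SD is 1.1 × √(1 − 0.85²) = 0.58 and the SE is 0.58 × √(2/100) = 0.082, so 0.23 is about 2.8 SE, the usual 80% power point. Varying the correlation (0.80 to 0.90) or the arm size (60 to 150) at that one shift gives gains of 24 to 47 points. Reading this as a general gain is not supported, because smaller shifts give far less.

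**Category as the wrong outcome.** This is not supported either. Category does better when only heavier children respond and prevalence is 26%, though not clearly at 40%. The plan itself lists "possible program moderators: child age, child sex, child BMI status, and location", so it does not rule out such a response.

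**Nesting and the covariate.** The plan already says that ICCs "will be first examined for each dependent variable to determine if a statistical approach controlling for such nesting will be necessary", so nesting is not a gap. A reader might also infer that pretest BMI z-score would be both outcome and covariate. Weight status is excluded from the multilevel models, so that remains hypothetical.

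**Conclusion.** The concern holds as a conflict and a set of omissions, not as a fatal flaw. The multiplicity paragraph gives BMI a threshold and then restricts thresholds to a kind of test that the weight model does not contain. The visit, the two comparisons and the place of children below the 5th percentile are unstated, and no analysis of follow-up BMI z-score is described. These points follow from the text alone.

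The error figure of 9.75% requires two logits tested at 0.05 and independence; a single overall test at 0.05 would carry no inflation. The power figures depend wholly on assumed N, SD, correlation and effect. They show that BMI z-score can add much, little or nothing, which supports reporting it beside category and not in its place. No section names weight as the primary outcome, and nothing in the documents shows that a visit or comparison was chosen after the results were seen. The change should be made, at moderate priority.

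**What to change.** - Name one visit for the weight analysis.
- State which two BMI comparisons were intended, ruling parent BMI in or out, and apply 0.025 to the condition effect in each. Amend the sentence that confines thresholds to time effects accordingly.
- Place children below the 5th percentile in the lowest category, so that every randomised child with weight data is analysed. The plan also says "The main analyses will be conducted on participants who have data at all 4 time points"; state whether this binds a single-visit model, which needs only pretest and that visit.
- Report the weight result whatever its p value.
- Add child BMI z-score at the same visit as a continuous outcome, testing condition with adjustment for pretest BMI z-score, sex and age, and with the plan's own ICC check for nesting. Give it a 0.025 share only if category plus BMI z-score was the intended pair; otherwise label it supportive.
- Date the change and call it post hoc, because the protocol is dated March 2022 and cites pre-post results.

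The cost is SAP wording and one more model on a variable that the plan already derives. The post hoc label lowers the weight that the added result can carry. The two analyses may disagree, and both must then be shown. If alpha is shared, the category test loses about 10 points of its own power compared with testing at 0.05: in the base case at 26% prevalence, 33% to 23% for a shift of 0.23 in all children, and 46% to 35% for 0.5 in heavier children only.
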